8.2.4 CULTURAL ASSESSMENT

Culture is assessed at baseline using the Cultural Factor Survey, a validated, psychometrically sound questionnaire consisting of three subscales: temporal orientation (5 items), collectivism (6 items), and religiosity (9 items)⁴⁷. Prior PN studies have used these scales to measure cultural factors⁴⁸. Items are scored on a 4-point Likert scale from 'Strongly Disagree' (1) to 'Strongly Agree' (4). Scores on each sub-scale range from 5-20 (temporal orientation), 6-24 (collectivism), and 9-36 (religiosity). Higher scores on each subscale indicate greater amounts of each of the measured construct. Scores as reported as the total score for each of the three individual subscales.

8.3 NON-BASELINE CLINICAL CHARACTERISTICS

Additional oncologic details related to the course of clinical care will be collected from the EMR. For patients receiving portions of their care outside of MUSC, appropriate clinical records will need to be collected.

Additional non-baseline oncologic characteristics include date of definitive surgery, type of ablative surgery, type of surgical reconstruction, AJCC 8th edition pathologic TNM Class, AJCC 8th edition overall pathologic stage grouping, adverse pathologic features (margin status, perineural invasion, extranodal extension), facility delivering the adjuvant therapy, planned radiation dose (Gy), delivered radiation dose (Gy), presence (and type) of chemotherapy, date of completion of radiation therapy.

8.4 ENDPOINT AND OTHER NON-SAFETY ASSESSMENTS

8.4.1 FEASIBILITY ASSESSMENTS

NDURE Accrual Rate is defined as the proportion of eligible patients who enroll in NDURE

NDURE Completion Rate is defined as the proportion of enrolled patients who complete the baseline assessment, at least two NDURE intervention sessions, and the final follow-up assessment

8.4.2 ACCEPTABILITY ASSESSMENTS

Satisfaction with the Interpersonal Relationship with the Navigator (PSN-I) Scale: The PSN-I is a 9-item measure of the satisfaction of the interpersonal relationship with the patient navigator. This reliable and validated measure^{49,50} has been widely used in prior studies of PN. The total score of the measure ranges from 9 (minimum) to 45 (maximum); higher scores represent a better outcome (greater satisfaction with the interpersonal relationship with the navigator).

8.4.3 NAVIGATOR CASELOAD

Information about navigator caseload is self-reported by the Navigator into the eCRF.

Navigator Caseload is the number of simultaneous cases (on-trial participants) being navigated by the NDURE navigator

Navigator Time Allocation (Direct) is the time (in minutes), that the NDURE navigator spends directly interacting with the patient to identify and address barriers to timely, equitable PORT

Navigator Time Allocation (Indirect) is the time (in minutes), that the navigator spends generating and documenting the NDURE PORT Care Plan or performing other forms of documentation in the EMR

Navigator Time Allocation (Asynchronous) is the time (in minutes), that the NDURE navigator spends enacting the NDURE PORT Care Plan to decrease barriers to care that is neither face-to-face with the patient nor time documenting in the EMR. Examples of asynchronous time include making phone calls to schedule appointments, faxing referrals, reviewing the path report, and making phone calls to patient for referral tracking.

Navigator Time Allocation (Total) is the sum of the time, in minutes, of the direct, indirect, and asynchronous navigator time.

8.4.4 EFFICACY ASSESSMENTS

Data for the efficacy assessments described below are gathered from the EMR. For participants who receive care at a non-MUSC facility (and thus whose information is not in the MUSC EMR), records will be requested for the treating facility at the conclusion of adjuvant therapy and scanned into MUSC EMR.

PORT Delay: The initiation of PORT more than 6 weeks (42 calendar days) from the date of the definitive surgical resection.

- If the surgical management of the primary tumor and the neck are staged (i.e. occur on two different calendar days), the date of the definitive surgery for the primary tumor will be used.
- If additional surgical resection is required (e.g. re-resection of positive margins to clear residual disease), the date of the earlier (i.e. attempted definitive) surgical procedure will be used to determine the date of definitive surgical resection.
- Patients who suffer a mortality prior to initiating PORT and > 6 weeks after surgery will be assessed as having a PORT delay.

- Patients who suffer a mortality prior to initiating PORT and \leq 6 weeks after surgery will be non-evaluable for evaluation of the primary endpoint of PORT delay.
- Patients who recur prior to initiating PORT, regardless of the timing of the recurrence relative to 6 weeks postoperatively, will be assessed equivalently to patients who do not recur for the purposes of this endpoint.

Time-to-PORT (TTP): The time, in days, between the date of definitive surgical resection to the initiation of PORT. All of the criteria used to adjudicate the date of the definitive surgical procedure described for the primary outcome measure will be applied to this measure.

- For patients who are alive and have not initiated PORT by 18 weeks (126 days) from surgery, TTP will be censored at this timepoint.
- For patients who suffer a mortality prior to initiating PORT and $<$ 18 weeks after surgery, TTP will be censored at the date of death. (A sensitivity analysis treating death as a competing risk will be performed, as described in Section 9.4)
- For patients who recur prior to initiating PORT, regardless of the timing of the recurrence relative to 18 weeks postoperatively, TTP will be assessed equivalently to patients who do not recur.

8.4.5 BARRIER TO TIMELY PORT ASSESSMENTS

Perceived Barrier Questionnaire-Patient (PBQ-P): The PBQ-P is a 17-item self-report measure of barriers to timely initiation of PORT, as assessed by the patient. Each item is scored as yes/no. Versions of this questionnaire have been used extensively to assess perceived barriers in prior PN studies^{11,44,51,52}. Each item is scored as yes/no. The total score is calculated by summing the individual responses. PBQ-N scores range from 0-17; higher scores reflect greater barriers to timely PORT.

Perceived Barriers Questionnaire-Navigator (PBQ-N): PBQ-N is a 17-item measure of barriers to timely initiation of PORT, as assessed by the PN. Each item is scored as yes/no. Versions of this questionnaire have been used extensively to assess perceived barriers in prior PN studies^{11,44,51,52}. Each item is scored as yes/no. The total score is calculated by summing the individual responses. PBQ-P scores range from 0-17; higher scores reflect greater barriers to timely PORT.

8.4.6 CANCER CARE DELIVERY PROCESS ASSESSMENTS

A Cancer Care Delivery Process form is included as the eCRF and will be completed by the program coordinator using information from the EMR.

Pre-Surgical Radiation Consultation is defined as the attendance by the patient at a consultation with the treating radiation oncologist (at MUSC or elsewhere) prior to surgery to discuss RT in the definitive or adjuvant setting. Patients who see a radiation oncologist at one facility prior to surgery but receive PORT at a different facility are evaluated as 'no' for this measure.

Pre-Radiation Therapy Dental Evaluation is defined as the evaluation by a dentist for pre-radiation dental extractions. Edentulous patients are non-evaluable for this measure. Dentulous patients who do not have a pre-surgical dental evaluation are evaluated as 'no'.

Pre-Radiation Extractions of Indicated Teeth with Definitive Surgery is defined as the extraction of indicated carious/non-restorable teeth either prior to or during definitive surgery. Patients who have a dental evaluation that indicates the need for extractions, but for whom teeth are not extracted prior to or during

surgery are evaluated as 'no' for this measure. Edentulous patients and dentulous patients who have a dental evaluation and extractions are not recommended are not evaluable for this measure.

Time from Surgery to Pathology Report is defined as the production of the pathology report from the definitive surgical procedure within the EMR. Addenda to the pathology report at the request of the HNSCC team (e.g. tumor p16 status) are not counted in this measure.

Time from Surgery to PORT Referral is defined as the time, in days, from the date of the definitive surgical procedure to the date the referral (or postoperative appointment) is placed to discuss adjuvant therapy with the treating radiation oncologist. For patients who have seen a radiation oncologist prior to surgery, this metric refers to the scheduling of the post-operative follow-up appointment with the radiation oncologist. In situations in which a patient is re-referred postoperatively (i.e., a patient is referred to a radiation oncologist at one facility and then decides to get treatment at a different facility), the measure is evaluated using the time to the second referral.

Time from Surgery to Postoperative Appointment with Radiation Oncology is defined as the time, in days, from the date of definitive surgery to the date that the patient attends a postoperative appointment with radiation oncology. For patients who have seen a radiation oncologist prior to surgery, this measure refers to the scheduling of the post-operative follow-up appointment with the radiation oncologist. In situations in which a patient is re-referred postoperatively (i.e., a patient is referred to a radiation oncologist at one facility and then decides to get treatment at a different facility), the measure is evaluated using the time to the second referral. In situations in which an appointment is scheduled but the patient does not attend the appointment, the measure is evaluated using the date for which the appointment was actually attended.

PORT Duration, defined as the number of days from the initiation of PORT to the completion of PORT among patients who complete the intended course of adjuvant therapy.

Completion of intended course of PORT, defined as receipt of the planned PORT dose (total Gy).

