To evaluate the preliminary clinical impact of NDURE compared with UC on delays starting PORT among white and AA HNSCC patients.	PORT delay, defined per National Comprehensive Cancer Network Guidelines as the initiation of PORT > 6 weeks (42 days) following definitive surgery for HNSCC.
Secondary	
To evaluate the preliminary clinical impact of NDURE compared with UC on time-to-PORT among white and AA HNSCC patients.	Time-to-PORT initiation, defined as the number of days from the date of definitive surgery for HNSCC to the date of initiation of PORT. Treatment package time, defined as the number of days from the date of definitive surgery for HNSCC to the date of PORT completion.
To evaluate the preliminary clinical impact of NDURE compared with UC on racial disparities in delays starting PORT among white and AA HNSCC patients.	PORT delay, defined per National Comprehensive Cancer Network Guidelines as the initiation of PORT > 6 weeks (42 days) following definitive surgery for HNSCC. Time-to-PORT initiation, defined as the number of days from the date of definitive surgery for HNSCC to the date of initiation of PORT.

Table 2. Study Objectives and Endpoints

	Treatment package time, defined as the number of days from the date of definitive surgery for HNSCC to the date of PORT completion.
To evaluate the preliminary impact of NDURE compared with UC on cancer care delivery processes.	Pre-surgical radiation consultation, defined as the attendance by the patient at a consultation with the treating radiation oncologist prior to surgery to discuss radiation therapy in the definitive or adjuvant setting.
	Pre-RT dental extractions, defined as the extraction of indicated carious/non-restorable teeth prior to or during definitive surgery.
	Time from surgery to PORT referral, defined as the time, in days, from the date of the definitive surgical procedure to the date the referral (or postoperative appointment) is placed to discuss adjuvant therapy with the treating radiation oncologist.
	Time from surgery to postoperative appointment with radiation oncology, defined as the time, in days, from the date of the definitive surgical procedure to the date that the patient attends a postoperative appointment with radiation oncology
Exploratory	

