Function 4: Improve communication between patient and providers regarding intentions and goals for timely, guideline-adherent PORT.

Form: Standardized discussion of expected indication for PORT and choice of radiation facility at initial consultation. At the initial surgical consultation, the clinician informs the patient that based on his/her clinical stage, it is expected that treatment will include a package of surgery and PORT. At this same clinical encounter, the NDURE navigator facilitates a discussion with the patient and clinician to help the patient decide at which facility he/she will receive PORT.

Function 5: Enhance coordination of care between healthcare teams during care transitions and about treatment sequelae.

Form: NDURE PORT Care Plan. At each navigation encounter, the NDURE navigator meets with the patient, caregiver, and clinicians to generate (and update) a PORT Care Plan. The NDURE PORT Care Plan is an EMR-based document that (a) captures clinical factors and the care delivery processes necessary to start PORT; (b) describes the patient's barriers to timely PORT; and (c) documents the patient's personalized Barrier Reduction Plan.

Function 6: Restructure the organization to clarify roles and responsibilities for care processes associated with PORT delivery to avoid duplication and gaps in care.

Form: NDURE Navigator makes referrals and schedules appointments to optimize adherence with key PORT care delivery process. The NDURE navigator is assigned sole responsibility for making all PORT-related referrals (and scheduling appointments) with radiation and medical oncology, dentistry, and oral surgery in a manner that optimizes adherence to the following care delivery processes associated with timely PORT.

- (1) Prior to surgical resection, the patient has consultation with a radiation oncologist at the facility where the patient intends to receive PORT.
- (2) Prior to surgical resection, the patient has a consultation with a dentist and oral surgeon (if indicated) and subsequently undergoes extraction of indicated teeth at the time of surgical resection.
- (3) Engaging with the pathologist if the pathology report is not issued by postoperative day 8. Upon receipt of the pathology report, promptly communicating key pathologic findings to the HN team to facilitate formation of a plan for pathology-directed adjuvant therapy.

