Care delivery processes	
NDURE Navigator is assigned sole responsibility for making referrals and scheduling appointments to optimize adherence with care delivery processes associated with timely PORT. The NDURE navigator is assigned sole responsibility for making all PORT-related referrals (and scheduling appointments) with radiation and medical oncology, dentistry, and oral surgery in a manner that optimizes adherence to the following care delivery processes associated with timely PORT.
 
(1) Prior to surgery, the patient has consultation with a radiation oncologist at the facility where the patient intends to receive PORT.
 
(2) Prior to surgical resection, the patient has a consultation with a dentist and oral surgeon (if indicated) and subsequently undergoes extraction of indicated teeth at the time of surgical resection.
 
(3) Engaging with the pathologist if the pathology report is not issued by postoperative day 8. Upon receipt of the pathology report, promptly communicating key pathologic findings to the HN team to facilitate formation of a plan for pathology-directed adjuvant therapy.
 
(4) Scheduling appointments with radiation oncology +/- medical oncology within 10 days of surgery as directed by the HN team.
 
(5) Ensuring that the postoperative appointment with radiation oncology is scheduled within 10 days of when the referral was placed.
	
Variable roles and responsibilities of Head and Neck care team members to optimize adherence with care delivery processes associated with timely PORT. A variable combination of residents on the inpatient head and neck service and outpatient advanced practice providers and nurses (but not the head and neck nurse navigator) are responsible for making referrals and scheduling appointments for radiation oncology, medical oncology, dental oncology, and oral surgery without specific attention to optimizing adherence to the following care delivery processes associated with timely PORT.

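### Section 8.4.6 defines time to the postoperative radiation-oncology appointment inconsistently (attendance, scheduling, second referral); read literally, it would tend to favour NDURE

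*Combined protocol and SAP*

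**What the plan says.** Table 2 (Section 3) runs this endpoint from definitive surgery "to the date that the patient attends a postoperative appointment with radiation oncology", with no exception. The lead sentence in Section 8.4.6 agrees: "from the date of definitive surgery to the date that the patient attends a postoperative appointment with radiation oncology". Three further rules follow in the same paragraph of 8.4.6:

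- One rule covers those who "have seen a radiation oncologist prior to surgery, this measure refers to the scheduling of the post-operative follow-up appointment".
- For patients re-referred to another facility after surgery, "the measure is evaluated using the time to the second referral".
- For patients who miss a scheduled visit, "the measure is evaluated using the date for which the appointment was actually attended".

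The PORT-referral endpoint, defined just before it, has the same re-referral rule and a nearly identical sentence for patients seen before surgery: "this metric refers to the scheduling of the post-operative follow-up appointment with the radiation oncologist". There it plainly means the act of booking.

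On the arms, Function 6 in Section 6.1.1.1 lists as a care process for the NDURE navigator to optimise: "Prior to surgical resection, the patient has consultation with a radiation oncologist at the facility where the patient intends to receive PORT". The usual-care column of Table 3 says referrals and appointments are made "without specific attention to optimizing adherence to the following care delivery processes associated with timely PORT". Section 9.4.4.2 analyses the endpoint like the other time-to-event endpoints, with adjustment only for the stratification variables.

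**The concern.** One endpoint has three possible stopping events: attendance, scheduling and second referral. Booking cannot come after the visit it books, so the scheduling clause can only shorten a patient's time. It applies to patients already seen by a radiation oncologist before surgery, a state that arises after randomisation and that NDURE sets out to produce. If NDURE succeeds there, more of its patients are scored at the earlier event, and the arms can separate on this endpoint even when postoperative visits occur on the same days.

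For patients seen before surgery, the literal rule also makes this endpoint nearly the same quantity as the PORT-referral endpoint. If the follow-up visit was booked before surgery, the rule gives a zero or negative time, and no handling is stated. The program coordinator abstracts these dates from the medical record in a non-blinded trial, so an unclear rule may be applied differently from patient to patient.

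**Working it through.** **Figures in the plan.** The plan gives no figure for this endpoint. Its only related figure is power for PORT delay (Section 9.2.2): 75 per arm, 45% versus 25%, two-sided alpha 0.10. With a pooled proportion of 0.35, the null standard error is sqrt(2 × 0.35 × 0.65 / 75) = 0.0779. The alternative standard error is sqrt((0.45 × 0.55 + 0.25 × 0.75) / 75) = 0.0762. Power is Φ((0.20 − 1.645 × 0.0779) / 0.0762) = 82.7%, against 83% stated. This confirms the design inputs used below and nothing more.

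**Size on the literal reading.** If attended dates have the same distribution in both arms:

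artefact in mean days = (NDURE rate − usual-care rate of pre-surgical consultation) × (days from scheduling to attendance)

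Neither factor is in the documents. The assumed ranges are a rate difference of 30 to 60 points and a gap of 5 to 10 days. The only related figure is NDURE's own target in Function 6, item 5, of 10 days from referral to appointment. That is a process target, not an observed interval.

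- Low: 0.30 × 5 = 1.5 days
- High: 0.60 × 10 = 6 days

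**Effect on the test.** A simulation used 75 per arm and 1,000 runs per scenario. Attended times were identical in distribution (assumed gamma, mean 21 days, SD 7). The log-rank test was unstratified and uncensored, at two-sided 0.10. Patients with a pre-surgical consultation were scored at the attended date minus the gap.

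| Consultation rate, NDURE vs usual care | Gap (days) | Rejection rate | Mean difference (days) |
|---|---|---|---|
| 50% vs 50% | 10 | 12.7% | 0.0 |
| 60% vs 40% | 5 | 17.7% | −1.0 |
| 60% vs 40% | 10 | 33.2% | −1.9 |
| 80% vs 40% | 3 | 23.7% | −1.2 |
| 80% vs 40% | 5 | 45.6% | −2.0 |
| 80% vs 40% | 10 | 84.2% | −4.0 |
| 90% vs 30% | 5 | 75.3% | −3.1 |
| 90% vs 30% | 10 | 99.7% | −6.0 |

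Negative values favour NDURE. With unequal rates, nearly all rejections did so. The equal-rates row splits evenly between arms (6.2% favouring NDURE). It lies somewhat above the nominal 10% (simulation error about sqrt(0.1 × 0.9 / 1,000) = 0.95 points), so the other rows are best read against 10 to 13%. Section 9.4.1 names 0.05 for inferential tests; rejection rates at that level would be lower.

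**Re-referral clause.** Table 3 says that in usual care the choice of radiation facility is not discussed before surgery. Re-referral may therefore be more common there (an inference), and the second referral precedes the visit it leads to. Suppose re-referral is 20% in usual care and 5% in NDURE, with consultation 80% vs 40%. The share scored early is then 1 − 0.20 × 0.95 = 0.81 in NDURE and 1 − 0.60 × 0.80 = 0.52 in usual care, a difference of 0.29.

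- 5-day gap: 0.29 × 5 = 1.45 days (simulated −1.5; rejection 29.6%, down from 45.6%)
- 10-day gap: 0.29 × 10 = 2.9 days (simulated −2.9; rejection 64.7%, down from 84.2%)

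An extreme case removes the effect. With re-referral 40% vs 0%, consultation 60% vs 40% and a 10-day gap, the shares are 0.60 in NDURE and 1 − 0.60 × 0.60 = 0.64 in usual care. The difference is 0.04 × 10 = 0.4 day, now favouring usual care, with rejection at 11.6%.

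**The case against.** The strongest reply is that the clause only says which visit counts. For a patient already seen before surgery, it would point to the postoperative follow-up and not the earlier consultation, with scheduling meaning the day the visit is set for. Table 2 and the lead sentence both use attendance. The schedule of activities collects the postoperative appointment date separately from the referral date. The missed-visit sentence would have little purpose for these patients if booking had already stopped the clock. Function 6, item 5 also seems to use the word for the date of the visit. On this reading the bias from the clause largely disappears. The reading is plausible, but the nearly identical sentence in the PORT-referral definition means booking, and the re-referral clause departs from attendance on any reading. The text still needs correcting.

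Other limits also stand. Consultation before surgery is a process NDURE aims to optimise, not a requirement. The trigger is having seen any radiation oncologist, which is broader than Function 6's consultation at the intended facility, so the arms may differ less on the trigger than on that process. The same rule applies to both arms, and any imbalance is indirect. The re-referral clause may work in the opposite direction.

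A reader might infer that the endpoint favours NDURE by construction. The documents do not support that: it needs the literal reading, a higher consultation rate under NDURE, and no full offset from re-referral.

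**Conclusion.** The definition is internally inconsistent and should be corrected. Followed literally, it ties the event to a post-randomisation state that NDURE targets and would tend to make NDURE look faster with no true difference in attended dates. The 1.5 to 6 days is before any re-referral offset and rests wholly on the assumed consultation rates and gap. The rejection rates also rest on an assumed distribution of attended times and a simplified test. None of these is an estimate for this trial.

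A reader might also infer that the whole care-delivery objective would report an artefact. It would not: Table 2 lists four endpoints under that objective and this concerns one. PORT delay, time-to-PORT and treatment package time have their own definitions and are untouched. The point merits correction before this endpoint is analysed, but does not threaten the trial's main conclusions.

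**What to change.** In Section 8.4.6, replace the pre-surgical and re-referral clauses of this endpoint with one rule:

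*The event is attendance at the first radiation-oncology visit after surgery, for every patient, whether or not a radiation oncologist was seen beforehand; a pre-surgical visit does not count. If the patient is re-referred to a second facility, the event is the first postoperative visit attended there.*

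The missed-visit sentence can stay, since it already agrees. Keep scheduling and second-referral dates for the PORT-referral endpoint only, and align Table 2 and Section 8.4.6, including the rule for re-referred patients.

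The cost is a wording change to one definition. The postoperative appointment date is already on the schedule of activities, so no new data item is needed. The only downside is that some recorded times become longer.
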